1.2.3 Quality of NVB spare surgery and video assessment

The LAPPRO study highlights significant variation in functional and oncological outcomes among surgeons performing radical prostatectomy, emphasizing the influence of surgeon-specific factors such as experience, surgical technique and volume. These disparities persisted even after accounting for patient and tumour characteristics, again highlighting the influence of technique (30).

Heterogeneity in EF recovery seen suggests there are variations in surgical techniques employed by different surgeons. For instance, a recent study using video analysis of RARP revealed that the technique is not standardised among surgeons (31). Global evaluation of robotic skills during RARP through peer- reviewed video assessment has been demonstrated in previous studies (32). A validated tool, prostatectomy assessment and competency evaluation (PACE) has been developed to evaluate the expertise of surgeons performing RARP (33). To our knowledge, there has not been an evaluation of the quality and grade of NVB preserving surgery to assess the relationship with functional outcomes using a structured framework.

A structured assessment of the surgical technique using the recorded videos will help identify the techniques leading to better functional outcomes.

1.2.4 Preoperative mpMRI, mapping of pelvic vasculature and postoperative MRI

mpMRI is accepted as the gold standard for preoperative local staging of PCa. In addition to diagnosis and staging, mpMRI helps guide surgery and the degree of NVB sparing without impacting margin status (34).

Prior research in this area has focused on utilising the pre-surgical mpMRI information to predict the recovery of continence(35). For example, membranous-urethral length (MUL), measured using the preoperative mpMRI, is an established independent predictor for postoperative recovery of urinary continence (36,37). This information informs preoperative patient counselling and treatment decision-making. However, the literature on imaging markers to predict and mitigate the risk of ED in patients with PCa undergoing minimally invasive radical prostatectomy has not been summarised before.

We carried out a systematic review (PROSPERO; Registrations ID CRD 42022359557) to evaluate the possible application of imaging parameters to predict EF after RARP. Nevertheless, the variability of results, significant risk of bias, and inadequate study design in the available literature render the therapeutic use of the reported parameters of low utility. Good-quality, prospective research is needed to further evaluate a variety of imaging parameters as predictors of postoperative EF to ensure results are reproducible. There has been no assessment of accessory pudendal artery identification through imaging preoperatively and correlation of this to EF outcomes after surgery. The prevalence of accessory pudendal artery is 38.2% (8). In our studies at UCLH we were able to map the accessory pudendal arteries of men using prostate mpMRI (unpublished material). We are currently looking at identifying the accuracy of the mpMRI in identifying the APA (unpublished material).

Several studies have shown that vasculature of the pelvis can be mapped. Selective pudendal angiography can be used to demonstrate the presence of accessory pudendal arteries; however, this is an invasive procedure (38). Moreover, contrast enhanced MR angiography can be used to identify accessory pudendal arteries(39).

The dynamic contrast enhancement sequence is performed as part of the mpMRI for PCa diagnosis in everyday routine practice. This can be used to map the vasculature of the prostate identifying the presence of accessory pudendal arteries. In our study we will map the accessory pudendal arteries using the diagnostic prostate mpMRI. This information will be shared with surgeons to guide their surgery, and we will review the implications of EF recovery.

One study looked at difference in anatomical changes between preoperative and postoperative MRI scan in relation to postoperative urinary incontinence outcome(40). This helped outline the anatomical changes associated with better urinary function. In our study, by obtaining an additional MR angiogram at 3 months after surgery for patients who we detected an accessory pudendal artery, we will be able to assess whether the accessory blood supply to the penis was preserved or injured and assess its correlation with EF recovery.

1.2.5 Standard of care for ED after RARP

Penile rehabilitation is the term often used to describe the treatment for ED after PCa treatment. The standard of care for the treatment of penile rehabilitation after RARP is a stepwise approach. Initially, all patients are offered phosphodiesterase 5 inhibitors (PDE5i) in the form of either tadalafil or sildenafil. Alongside this, penile rehabilitation using a vacuum erection device is recommended to maintain penile length and offers an opportunity for motivated patients to resume sexual activity with the application of the ring. Patients with persistent ED despite medical treatment are offered second line treatment in the form of ICI using alprostadil (PGE1) or Invicorp

EVERiST, EDGE (Sponsor) number 177704, IRAS number 335003, Protocol version 1.0, 07/10/2025

(Aviptadil/Phentolamine). This is self-administered by the patient in clinic setting after a tutorial in the andrology clinic. If the above measures fail, patients are ultimately offered penile prosthesis surgery however, this is after at least 18 months to allow for erectile recovery to take place after surgery.

1.2.6 Assessment of functional outcomes after RARP

A. Through Validated EF questionnaire

The assessment and treatment of ED has been greatly improved with the introduction of EF validated questionnaires over the last 3 decades namely the international index of EF (IIEF). Such questionnaires were designed to screen for ED and assess the efficacy of the oral medication in treating ED (41). Several forms of the IIEF are available and it includes an EF domain (IIEF-EFD), sexual desire domain, intercourse satisfaction and overall satisfaction domains. Another widely used bothersome score is the disease specific expanded prostate cancer index composite (EPIC) (42). The EPIC questionnaire was designed to assesses symptoms of PCa treatment including both radiotherapy and surgery sequelae.

B. Penile doppler assessment of erectile hemodynamics.

An objective method to assess EF is the use of penile dopplers ultrasound (PDUS). A study by Mulhall et al, conducted PDUS on patients who underwent bilateral NVB sparing radical prostatectomy, it was found that 32% of men exhibited normal erectile haemodynamics following the surgery (43). These 32% had a statistically significant higher IIEF scores, penile rigidity and functional erections allowing intercourse than those with abnormal haemodynamics.

A subset of patients exhibits evident vascular alterations following radical prostatectomy. Thus far, all studies have focused on either identification of accessory pudendal artery (19) or carrying out PDUS for the assessment of the vascular haemodynamic after surgery (43) but never in the same study as prior research was in the pre mpMRI era. Consequently, understanding the pudendal artery and its anatomical variations, along with their preservation in patients experiencing erectile dysfunction following RARP, necessitates an evaluation of whether penile circulation is likewise maintained. This will signify the presence of continuous neuropraxia and an expected recovery over time.

PDUS are carried out after an Intracavernosal injection (ICI) of an erection inducing medication mostly commonly alprostadil or Invicorp. As an optional part of the study, we will offer patients undergoing RARP a PDUS to assess their erectile hemodynamics before and after their surgery. For patients who fail to respond to first-line oral medication for ED, ICI medications are the second-line treatment for motivated patients. A PDUS can be carried out simultaneously to evaluate erectile hemodynamics which is currently the standard of care to investigate and prognosticate erectile dysfunction.

1.2.7 Summary

The proposed pathophysiology for EF is complex and likely involves both neurogenic and vasculogenic components. Despite advancement in surgical technique with the widespread adoption of robotic surgery, EF recovery after NVB bundle sparing surgery remains unclear. With the widespread adoption of the mpMRI, specifically the dynamic contrast enhancement sequence, radiologists can map the vasculature of the pelvis, and this information may be useful in guiding surgery and improving EF outcomes. Video recordings of robotic surgery also offer the opportunity to objectively assess the operative technique and correlate this to functional outcomes. Our objective is to enhance patient outcomes by furnishing surgeons with the necessary information regarding patient-specific accessory pudendal arteries, which will be mapped to facilitate surgery with preservation of these arteries.

The literature suggests that the quality of NVB sparing may be the cause of variation in EF recovery. (30). To ensure we capture this confounder in our outcome measurement of EF recovery we will assess the quality of the NVB sparing using a validated tool(33).

Measurement of EF recovery has also been a topic of debate and despite there are patients reported outcome measure tools namely EPIC-26 and IIEF-EFD we are unsure if these measures represent what patients value most(4). We therefore will capture EF recovery using validated tools and objectively using PDUS.

We believe that the pathophysiology of EF recovery following RARP is a combination of arterial supply impairment and neuropraxia. It is believed that neuropraxia recovery can persist for up to 24 months following RARP(44). Nevertheless, it is crucial for management purposes to ascertain whether the arterial supply is secure, and the gold standard measurement is a PDUS. This will be provided to our patients as an optional assessment.

1.2.7 Feasibility assessment

This study will assess the practicality, acceptability and feasibility to conduct a full-scale observational study to investigate the influence of imaging detected APA on the EF recovery after NVB sparing RARP. This study will set out to assess barriers in recruitment, rate limiting steps, and the feasibility of utilising the current preoperative mpMRI in detection of APA in patients undergoing RARP and the practicality of carrying out PDUS and postoperative MRI angiogram to assess APA patency. This will inform a future appropriately powered study examining the effect of APA preservation on dual assessed EF recovery after NVB sparing RARP.

2 AIM(S),OBJECTIVES, AND OUTCOMES

Theory:

The accessory pudendal artery is regarded as a supplementary supply to the corpus cavernosum, providing improved physiological support for erectile function through collateral arterial supply. This results in increased resilience to external stress, allowing patients with APA to better endure RARP-induced stress as compared to patients without APA.

Hypotheses

EVERiST, EDGE (Sponsor) number 177704, IRAS number 335003, Protocol version 1.0, 07/10/2025

Imaging-based detection of the APA will aid in its preservation and exhibit superior EF recovery compared to those without APA and those with APA that was not preserved after surgery.

Aims and Objectives	
aim	The primary aim of this feasibility study is to assess the practicality and acceptability of conducting a full-scale observational study to investigate the influence of imaging detected accessory pudendal arteries (APA) presence on erectile function (EF) outcomes after neurovascular bundle (NVB) sparing robot assisted radical prostatectomy (RARP).
Objectives	
Primary objectives	
 1. To evaluate the feasibility of recruiting and retaining patients for a study on APA preservation during RARP. 2. To assess the practicality of using pre-operative multi-parametric MRI (mpMRI) for identifying and mapping APAs.
Secondary objectives	
 1. To determine the feasibility of recording and analysing intraoperative videos for assessing APA preservation during RARP. 2. To explore the acceptability and completion rates of published validated erectile function outcome measures. 3. To estimate the prevalence of APAs in the study population and the proportion of cases where APA preservation is achievable. 4. To assess the feasibility of collecting quality of life data related to erectile function post-RARP. 5. To identify potential barriers to patient participation and follow-up in a full-scale observational study 6. To gather preliminary data on the variability of erectile function outcomes to inform sample size calculations for a future study.
Outcome Measures	
Primary end-points	
 1. Recruitment and Retention Rates 
 a) Percentage of patients who satisfy the eligibility criteria amongst patients who opted for RARP b) Percentage of patients consenting to participate (denominator= number of eligible patients approached) c) Percentage of participants completing the study (denominator=number of patients consenting for the study) 2. MRI Assessment Feasibility 
 -Time required for APA mapping on mpMRI 3. Intraoperative Video Analysis

	
 -Percentage of RARP procedures with complete, analysable video recordings (denominator= number of patients consenting for the study) -Time required for video analysis of APA preservation 4. Erectile Function Questionnaire Completion 
 -Completion rates of validated EF questionnaires such as the International Index of Erectile Function (IIEF) questionnaire & EPIC -26 sexual domain within patients consenting to join the study. -Time taken to complete the questionnaires 5. Post-operative MRI assessment feasibility 
 -Proportion of patients who accepted to have a 3-month follow-up MRI angiogram within patients consenting to join the study -Proportion of patients who have a patent APA 6. Baseline Penile Doppler US (PDUS) assessment feasibility 
 -Proportion of patients accepting to have a preoperative PDUS. -Proportion of patients who received a baseline Doppler scan. 7. Postoperative PDUS assessment feasibility 
 -Proportion of patients who accepted to have a postoperative PDUS -Proportion of patients who received a postoperative PDUS
Secondary end-points	
 1. APA Prevalence and Preservation 
 -Percentage of patients with identifiable APAs on mpMRI -Proportion of cases where APA preservation was achieved during RARP 2. Quality of Life Data Collection 
 -Completion rates of quality-of-life questionnaires related to erectile function -Patient-reported acceptability of quality-of-life assessments. 3. Barriers to Participation 
 -Number and nature of reported barriers to study participation -Reasons for declining participation or withdrawal from the study 4. Variability in Erectile Function Outcomes 
 -Mean and Standard deviation of IIEF scores at follow-up time points -Range of erectile function recovery times
Other outcomes	
 • Pad free and leak free rate at 12 months. • Clear surgical margin rate (CSM) • Tri-fecta (CSM, Continence & Erectile function)

[figure not shown]

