	
 • All patients will have arterial mapping to provide the surgeons with a surgical plan based on the preoperative mpMRI. • Video-recorded BL NVB sparing RARP performed by [name], [name], [name] or [name]. • All patients will receive the same penile rehabilitation plan that is the standard of care at UCLH. • Patients with an APA identified will be offered a postoperative MRI angiogram to assess patency of APA. • As an optional part to the study, patients will be offered a penile doppler before and/or after their surgery to assess erectile haemodynamics. • The feasibility study will be able to inform the barriers for recruitment in a future appropriately powered study.
STUDY TIMELINES	
Study Duration/length	2 years
Expected Start Date	December 2025
End of Study definition and anticipated date	December 2027 The end of the study is defined as the date of the final 12-month follow-up visit for the last recruited participant. Recruitment will stop once between 20 and 40 patients have been enrolled, and all participants will be followed for 12 months after surgery.
Key Study milestones	
Submission for REC and HRA approval
 
Acquire REC and HRA approval
 
Start recruiting patients
 
Complete full 40 patient data with follow-up up to 1 year.

FUNDING & OTHER	
Funding	Non-acquired.
Other support	Clinical research fellow- [name]
STORAGE of SAMPLES / DATA (if applicable)	
Human tissue samples	Non-applicable
Data collected / Storage	UCLH/ UCL one drive secure storage data storage
KEY STUDY CONTACTS	
Chief Investigator	[name] , Honorary Associate Professor [contact] [name]
Study Coordinator	
Sponsor	University College London
Funder(s)	Non
Committees	
Sub-contractors	Non-applicable
Other relevant study personnel	N/A

KEY ROLES AND RESPONSIBILITIES

SPONSOR: The sponsor is responsible for ensuring before a study begins that arrangements are in place for the research team to access resources and support to deliver the research as proposed and allocate responsibilities for the management, monitoring and reporting of the research. The Sponsor also must be satisfied there is agreement on appropriate arrangements to record, report and review significant developments as the research proceeds, and approve any modifications to the design.

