3.7 Assessment of the pelvic vasculature with a postoperative an MR angiogram

By obtaining an MR angiogram with an arterial phase after the surgery, we will be able to confirm whether there is blood flow in the accessory pudendal arteries after surgery. This additional MRI at least 3 months after surgery will be only offered to patients who have an accessory pudendal artery on their preoperative mpMRI. This will be useful to assess whether the APA patency after surgery has an effect on EF outcomes. If there is an incidental finding on this MRI relating recurrence, then the parent team and the CI will be notified promptly. This will lead to further appropriate action.

We will follow an established and validated protocol for MRI angiography on month 3 (described in Appendix)

3.8 Penile doppler US (optional): Objective assessment of EF using erectile haemodynamics.

Penile Doppler ultrasound (PDUS) is a well-established diagnostic tool for ED in specialist clinical practice. As an optional part to the study, we will offer patients an opportunity to assess their erectile haemodynamics prior to surgery through a PDUS. The APA presence, features or absence will be known through review of their preoperative mpMRI. With that knowledge, the optional PDUS before surgery will outline the effect of APA on the haemodynamics in healthy men with prostate cancer.

Patients who will not respond to PDE5i after surgery will be offered with a PDUS to evaluate the flow of penile arterial blood and to provide objective evidence that the underlying cause of ED is arterial.

This will be an optional part to the study and will be offered at 6 months or earlier if patients wish to have ICI to treat their ED. This is the accepted standard of care for the evaluation of post-RARP ED that is not responding to medical treatment.

The standard penile doppler US protocol will be followed for patients who opt for this assessment. Details of the protocol are provided in appendix.

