Blood tests: The metabolic assessment of ED includes testosterone, HbA1c and lipid profile biochemical profile. As part of routine post-surgical PCa follow-up all patients have a PSA tests done
EVERiST, EDGE (Sponsor) number 177704, IRAS number 335003, Protocol version 1.0, 07/10/2025

at 2 to 3 months and either 1 or 3 more until month 12 depending on cancer features. We will use these time points to obtain the blood samples required for assessment of ED. Hence, additional hospital visits will be avoided. These blood samples that will be requested are standard part of assessment of ED therefore not leading to additional NHS costs. If the metabolic ED blood panel is normal, this will not be repeated again. Any abnormalities in these will be communicated to the patient and their general practitioner and where necessary, treatment will be recommended i.e. if patients have a new diagnosis of diabetes, the patient and their general practitioner will be informed to repeat the test and start treatment if necessary. These will then be retrospectively recorded by the research team. No samples will be obtained or stored as part of this research.

Postoperative MRI: For patients that undergoing bilateral NVB sparing RARP, with an APA identified on their preoperative mpMRI, an additional MRI will be offered at least 3 months after surgery to assess whether the accessory artery was preserved or sacrificed.

Penile doppler US: For patients opting to undergo a PDUS before and after surgery, an additional hospital visit may be required prior to surgery to perform the preoperative PDUS. Postoperatively, if patients do not respond to oral medication treatment for ED, they will be offered a PDUS during the same visit as their tutorial for intracavernosal injection (ICI) therapy, minimizing the need for additional hospital visits.

This tutorial, conducted in the clinic, ensures patients are proficient in self-administering alprostadil or Invicorp to achieve an erection. This approach aligns with the current standard of care for patients unresponsive to oral medications. During the clinic session, a penile Doppler US will be performed in conjunction with ICI self-administration to assess erectile haemodynamics comprehensively.

Additional visits:

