11 ASSESSMENT AND MANAGEMENT OF RISK

-Data management risks are discussed in section 10.

-Video recordings: This will be done through the standard operating stack and require no additional steps to changes to standard care. Currently, the procedures are routinely recorded in the operating room for training purposes and to evaluate where improvements could be made. The management of the video data file is discussed in section 10.

-Hospital visits: for participating patients, an additional MR angiogram will be obtained postoperatively for study participants which will require an additional visit to the hospital. The remaining appointments will align with the standard andrology follow-up after radical prostatectomy.

-Penile dopplers (OPTIONAL) A penile doppler US will be offered to patients before and after surgery to assess the erectile machinery for study participants. This will be particularly useful for patients that fail to achieve satisfactory erections with medical treatment after surgery. A large proportion of patients that fail medical treatment and wish to escalate their erectogenic treatment will require injection treatment to the side of the penis. During the tutorial for this therapy, we will carry out a penile doppler ultrasound to assess their EF objectively and assess the blood flow to the penis.

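### Primary end-point 5 divides MR-angiogram acceptance by all consenting men, although only men with an APA are offered the scan, so the rate reported is APA prevalence times acceptance

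*Protocol*

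**What the plan says.** The study summary and section 2 define the first measure under primary end-point 5 in identical words: "Proportion of patients who accepted to have a 3-month follow-up MRI angiogram within patients consenting to join the study". The denominator is therefore fixed in the protocol as everyone who consents.

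The passages on who is offered the scan are narrower:

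- Summary, methodology key points: "Patients with an APA identified will be offered a postoperative MRI angiogram to assess patency of APA".
- Section 3.7: the additional MRI "will be only offered to patients who have an accessory pudendal artery on their preoperative mpMRI".
- Section 4, postoperative MRI: for men having bilateral nerve-sparing surgery "with an APA identified on their preoperative mpMRI, an additional MRI will be offered at least 3 months after surgery". The paragraph on additional visits in section 4 repeats the restriction.
- Section 1.2.4, and the data lists in sections 3.1 and 3.2, also tie the postoperative MRI to men in whom an APA was found.

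One passage reads more broadly. Section 11 says that "an additional MR angiogram will be obtained postoperatively for study participants".

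On frequency, section 1.2.4 cites an APA prevalence of 38.2%, and the lay summary speaks of up to a third of patients. The target is 20-40 participants. The log in section 3.1 counts men who both consent to and undergo the postoperative angiogram. It lists no count of men offered it.

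**The concern.** An acceptance rate should be the number who said yes divided by the number who were asked. Here the numerator can contain only men with an APA, while the denominator also contains men without one. Every man without an APA is scored as a non-acceptor although no one put the question to him.

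The result mixes two quantities that the future study needs separately: how common APAs are on mpMRI, and how willing men with an APA are to return for a further scan. Section 1.2.7 (feasibility assessment) names the practicality of the postoperative MR angiogram as something this study is meant to establish. A low figure on this end-point could reflect refusal, few APAs, or both. The protocol applies the right principle in end-point 1b, where consent is divided by the eligible patients who were approached.

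**Working it through.** The protocol gives no expected acceptance rate, threshold or sample-size calculation for this end-point, so there is no stated figure to reproduce. The check is on what the definition returns.

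**Inputs.** N = 20 to 40 (summary, section 3). APA prevalence p = 0.382 (section 1.2.4), with one third as an alternative (lay summary). Acceptance among men offered, a, is not given, so a range is shown.

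**What the end-point equals.** Expected acceptors = N × p × a. Dividing by N gives p × a, so the maximum, at a = 1, is p.

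| True acceptance a | Reported value at p = 0.382 |
|---|---|
| 100% | 0.382 × 1.0 = 38% |
| 80% | 0.382 × 0.8 = 31% |
| 50% | 0.382 × 0.5 = 19% |

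**How firm the 38% ceiling is.** The ceiling in any one sample is the share of men with an APA in that sample. Binomial 2.5th to 97.5th percentiles:

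| N | p | Expected with APA | 95% range | Ceiling of end-point |
|---|---|---|---|---|
| 20 | 0.382 | 7.6 | 4-12 | 20-60% |
| 40 | 0.382 | 15.3 | 9-21 | 22.5-52.5% |
| 20 | 1/3 | 6.7 | 3-11 | 15-55% |
| 40 | 1/3 | 13.3 | 8-19 | 20-47.5% |

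**One reported value, several meanings.** A result of 30% is what the end-point returns for 78.5% acceptance at 38.2% prevalence (0.382 × 0.785 = 0.30), for 100% acceptance at 30% prevalence, and for 50% acceptance at 60% prevalence.

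**The two denominators on the same data** (exact 95% intervals):

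| Data | As written | Among men offered |
|---|---|---|
| N = 40, 15 offered, 12 accept | 12/40 = 30% (17-47%) | 12/15 = 80% (52-96%) |
| N = 40, 15 offered, 15 accept | 15/40 = 37.5% (23-54%) | 15/15 = 100% (78-100%) |
| N = 20, 8 offered, 8 accept | 8/20 = 40% (19-64%) | 8/8 = 100% (63-100%) |

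In the first two rows the interval as written lies wholly below the acceptance rate observed among men offered. With 8 of 8 accepting, its upper limit is 64%.

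**The case against.** The best defence is that nothing is irrecoverable. Secondary end-point 1 reports the percentage of men with an identifiable APA in the same cohort, so dividing end-point 5 by that percentage gives approximate acceptance: in the first example, 30% / 37.5% = 80%. This largely stands, with two limits. Having an APA is not identical to having been offered the scan, because the offer comes at least 3 months after surgery and section 4 also ties it to bilateral nerve-sparing. The section 3.1 log also merges acceptance with receipt and has no offered count. A primary end-point should not need this reconstruction.

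A second defence is that section 11 describes the angiogram as being for study participants, which would fit the stated denominator. That is one general sentence in a risk section against several explicit restrictions, one of which says the scan is offered only to men with an APA. It does not rescue the definition, but it does need aligning.

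Three stronger readings are tempting, and the document does not support them:

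- A reader might infer that the study would wrongly declare the scan infeasible. The protocol attaches no progression threshold to this end-point, so no stated decision turns on the figure.
- A reader might extend the fault to the patency measure under end-point 5, or to post-operative penile Doppler (PDUS) under end-point 7. Neither states a denominator, so neither is wrong as written, and the analysis plan may settle both. The passages on who is offered post-operative PDUS do differ in scope: section 3.8 says "Patients who will not respond to PDE5i after surgery will be offered with a PDUS", while section 11 says "A penile doppler US will be offered to patients before and after surgery". They should be reconciled, but that does not make the end-point 7 denominator contradictory.
- A reader might size the group offered PDUS from the 1-year recovery range in section 1.2.2. Recovery there is not defined with respect to PDE5i use, and section 3.8 places the offer at 6 months or earlier, so no such figure follows.

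**Conclusion.** The stated denominator of primary end-point 5 is wrong for what it is meant to measure. As written, the end-point estimates APA prevalence times acceptance and cannot exceed the share of participants with an APA.

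The size depends on prevalence. The 38% ceiling is an expected value at the protocol's cited 38.2%, not a fixed cap, and it would be about 33% at the lay summary's upper figure. Section 1.2.4 also says that the accuracy of mpMRI in identifying APAs is still being examined, so the proportion found here is uncertain.

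The consequence is a misleading headline rate among the primary feasibility results. The protocol gives no basis for going further, to lost data or a reversed decision. It is still worth correcting before recruitment starts, because the denominator is written into both the summary and section 2, and offers that are not logged as they occur may be hard to reconstruct.

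**What to change.** 1. In the summary and section 2, define the first measure of end-point 5 as the number accepting the angiogram divided by consenting men with an APA on pre-operative mpMRI who were offered it.
2. In the section 3.1 log, record the men offered, accepting and receiving the angiogram as three separate counts.
3. Align the section 11 sentence on the MR angiogram with the APA-only offer in sections 3.7 and 4.
4. As a side point, reconcile the passages on who is offered post-operative PDUS.

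The cost is wording in three places and extra columns in a log that already exists. The statistical price is a smaller denominator: about 8 to 15 men expected, with 4 to 21 plausible across the planned sample sizes at 38.2% prevalence. Intervals will be wide, for example 52-96% for 12 of 15. That width reflects how much the study can say about acceptance. The narrower 17-47% for 12 of 40 is precision about a different quantity.
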